A study involving 119 healthy subjects investigated the combination of tDCS intervention with retrieval practice and found that the strong retrieval practice effect left no room for tDCS to improve memory performance[7]. The combination of single-session online tDCS with retrieval practice in healthy individuals and found that the memory performance of anodal stimulation was inferior to cathodal stimulation and sham stimulation [8]. We have already explored the role of continuous periodic tDCS combined with interim testing on spatial route learning in patients with schizophrenia in a previous study [9], and found that both the learning strategy and tDCS independently facilitated the ability of patients with schizophrenia to learn new information in spatial route learning, suggesting that the tDCS of L-DLPFC has a significant improvement effect. In contrast, targeted tDCS treatment may be more effective for memory-impaired populations such as schizophrenia [10]. Therefore, further investigation is needed to determine the effectiveness of combining tDCS and retrieval practice for semantic memory intervention in schizophrenia patients. From a theoretical perspective, this combination may have a dual activation effect because (1) tDCS stimulation can enhance activation levels of the L-DLPFC, improving its cognitive function impairment; (2) retrieval practice can not only help patients initiate semantic memory strategies and promote semantic elaboration but also actively activate the brain regions stimulated by tDCS, thereby producing a synergistic effect.

Therefore, this study aims to investigate whether combining tDCS with retrieval practice facilitates the maintenance of semantic memory and improvement of semantic organization by comparing the use of retrieval practice strategies in patients receiving anodal L-DLPFC stimulation, sham stimulation.

2. Methods

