2.2 Design

A mixed experimental design of 2 (Stimulation type: anodal stimulation, sham stimulation) \times 2 (Learning strategy: retrieval practice, restudy) \times 2 (Retention interval: Immediate recall, Delayed recall) was employed. Stimulation type was a between-subjects variable, while learning strategy and testing time were within-subject variables. The dependent variables were the correct recall rate and Adjusted Ratio of Clustering (ARC) scores in the testing phase.

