2.4 Procedure

Treatment was administered by two examiners, and after a total of 10 sessions over 5 consecutive days, a final group of 52 patients participated in the learning and testing phase. Among them, 27 received anodal stimulation, while 25 received sham stimulation. Each participant of each stimulation type was involved in both learning conditions, meaning that all participants completed both retrieval and restudy learning and testing (experimental procedure in **Figure 1**).

(1) Stimulation phase

In the anodal group, the anode was placed over the left DLPFC (F3), and the cathode was placed over the contralateral supraorbital area (FP2). A direct current of 2mA was applied for 20 minutes during each stimulation session. Stimulation was conducted twice a day, at 9 a.m. and 2 p.m., for 5 consecutive days, totaling 10 sessions. In the sham group, the stimulation parameters, including the stimulation site and duration, were identical to those of the anodal group. However, during the 10-second ramp-up and ramp-down periods before and after stimulation, patients were unaware that the current was turned off.

(2) Learning phase

The experimental procedure followed the classic retrieval practice paradigm, which included a learning phase and a final test phase.

During the experiment, participants were informed that they would learn two lists of words. Subsequently, they might either learn the words again or complete a list recall test, and will be given a final test shortly thereafter. The learning of the retrieval practice list and the restudy list was conducted in a randomly balanced manner. Each word was presented for 5 seconds, with a 500-millisecond interval between words. To avoid providing secondary retrieval cues between examples, all words were shuffled pseudo-randomly within categories. Each list contained 17 words, consisting of 5 examples from each of the 3 experimental categories (15 experimental examples, 2 filler examples). The first and last words presented in each list were filler words, thus controlling for the primacy and recency effects on memory.

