For the retrieval practice list, participants underwent two learning sessions and two retrieval sessions (S-T-S-T). During retrieval, participants were instructed to write down all the words they had just remembered within 5 minutes. For the restudy list, participants underwent four study sessions (S-S-S-S). Between each learning cycle, participants completed a 3-minute simple arithmetic task (dispersed attention task).

(3) Testing phase

Immediate Test: Participants were instructed to recall as many words as possible from the learned lists within 10 minutes after completing all learning tasks.

Delayed Test: Participants were informed to recall as many words as possible from the

learned lists within 10 minutes 24 hours later.

[figure not shown]

Figure 1. Experiment procedure.

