2.5 Date scoring & analysis

The experimental results were processed using SPSS 26.0. The correct recall rate of word lists was calculated for each subject by the experimental assistant. Then, Free recall organization was measured by the Adjusted Ratio of Clustering (ARC) scores [14,15]. ARC scores range from 1 to 1. A 0 score indicates a level of clustering similar to what would be expected by chance, and a score of 1 implies perfect clustering. Negative values of ARC scores mean atypical and uninterpretable recall patterns[16]. For that reason, negative scores were excluded from analyses.

A mixed-design analysis of variance (ANOVA) was conducted to compare the correct recall rates and ARC clustering scores between the two learning strategies under two stimulation conditions. All statistical tests were performed at a significance level of 0.05, and post-hoc comparisons were adjusted using Bonferroni correction. Effect sizes were reported using partial eta-squared (η_p^2 ; ANOVAs).

3. Study Status

Record Verification: July 2024

Overall Status: Completed

Study Start: July 24, 2023 [Actual]

Primary Completion: January 30, 2024 [Actual]

Study Completion: April 15, 2024 [Actual]

List of abbreviations

tDCS transcranial direct current stimulation

L-DLPFC left dorsolateral prefrontal cortex

VLPFC ventrolateral prefrontal cortex

ARC Adjusted Ratio of Clustering

References

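### Dropping every negative ARC score biases the clustering outcome upward, most where fewest words are recalled

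*Protocol*

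**What the plan says.** Protocol section 2.2 makes clustering an outcome in its own right: "The dependent variables were the correct recall rate and Adjusted Ratio of Clustering (ARC) scores in the testing phase". The last paragraph of the Introduction asks whether the combined intervention "facilitates the maintenance of semantic memory and improvement of semantic organization"; ARC is the natural measure of the second half of that aim.

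Section 2.5 fixes the scale: "A 0 score indicates a level of clustering similar to what would be expected by chance", with 1 as perfect clustering. It continues: "Negative values of ARC scores mean atypical and uninterpretable recall patterns". The consequence drawn is: "For that reason, negative scores were excluded from analyses".

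The scores then enter a mixed-design ANOVA. On its factors, section 2.2 says: "Stimulation type was a between-subjects variable, while learning strategy and testing time were within-subject variables". Each patient therefore contributes up to four ARC scores (2 strategies × 2 intervals). The protocol does not say how many scores were dropped, whether a negative score removes one cell or the whole patient, or whether an analysis with all scores was run.

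**The concern.** The reason given for the exclusion does not fit the scale the section has just defined. If zero is the chance expectation, scores below zero are what chance produces about half the time. They are also the scores showing the least semantic organisation, which is what the study wants to measure.

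The rule selects on the value of the outcome, after randomisation, and in one tail only. Three consequences follow.

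- Mean ARC rises whenever any score is negative.
- The rise depends on how many words were recalled, because ARC varies more when few words are scored. Recall may well differ between retrieval practice and restudy, between the immediate and 24-hour tests, and between arms. A pure recall difference can then appear as an ARC difference, with the lower-recall condition looking better organised.
- At equal recall, the condition with weaker clustering loses more scores, so a true clustering difference shrinks.

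If the ANOVA also needs all four cells per patient, one negative score could remove the patient. The correct recall rate is not affected.

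**Working it through.** The protocol gives no exclusion count or ARC value to reproduce, so the check works from its list structure.

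**Inputs from the protocol.** Section 2.4: "Each list contained 17 words, consisting of 5 examples from each of the 3 experimental categories", so 15 scored words in 3 categories of 5, with 2 fillers. The same section gives 52 patients tested. Section 2.2 gives four cells per patient.

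**Assumptions.** Recall level and clustering strength are not in the document and are varied below. ARC is taken in its standard form, which agrees with the protocol's anchors of 0 and 1:

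ARC = (R − E) / (max − E), with E = Σnᵢ²/N − 1 and max = N − k,

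where R is the number of adjacent same-category pairs, N the words recalled, nᵢ the words from category i, and k the categories recalled. It is undefined when max = E or N < 2.

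**Step 1: an exact case.** Suppose a patient recalls 6 words, 2 per category. Then E = 12/6 − 1 = 1, max = 6 − 3 = 3, and ARC = (R − 1)/2. There are 6!/(2!·2!·2!) = 90 equally likely category orders if recall is random: 30 with R = 0, 36 with R = 1, 18 with R = 2 and 6 with R = 3.

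- All scores: (30 × −0.5 + 36 × 0 + 18 × 0.5 + 6 × 1)/90 = 0.
- Negatives dropped: (0 + 9 + 6)/60 = 0.25.

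With all 15 words recalled, E = 75/15 − 1 = 4, max = 12, and ARC = (R − 4)/8. A score one pair below chance (−0.125) is dropped; one pair above (+0.125) is kept.

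**Step 2: same clustering, different recall.** Each word is recalled with probability p. Recall order is drawn with same-category words weighted 1 (chance), 3 or 6; 20,000 draws per setting, scored per list.

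| Clustering | All scores, 40% vs 70% recall | Negatives dropped, 40% vs 70% | Gap, all → retained |
|---|---|---|---|
| Chance | 0.01 vs 0.00 | 0.49 vs 0.24 | 0.01 → 0.25 |
| True ARC about 0.4 | 0.42 vs 0.39 | 0.63 vs 0.44 | 0.03 → 0.19 |
| True ARC about 0.6 | 0.64 vs 0.60 | 0.75 vs 0.62 | 0.04 → 0.13 |

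**Step 3: different clustering, same recall (50%).**

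| Clustering | Negative share | Mean, all | Mean, retained |
|---|---|---|---|
| Chance | 0.489 | −0.002 | 0.360 |
| About 0.4 | 0.144 | 0.409 | 0.537 |
| About 0.6 | 0.050 | 0.624 | 0.678 |

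Chance versus about 0.4: 0.409 + 0.002 = 0.411 becomes 0.537 − 0.360 = 0.177. About 0.4 versus about 0.6: 0.624 − 0.409 = 0.215 becomes 0.678 − 0.537 = 0.141.

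**Step 4: patients kept if all four cells are required.** With independent cells this is (1 − negative share)⁴: 0.511⁴ = 0.07, 0.856⁴ = 0.54 and 0.950⁴ = 0.81, or about 4, 28 and 42 of 52. A majority is lost only above 1 − 0.5^(1/4) = 15.9% negative per cell. Correlation within patients reduces the loss: at 15% negative, 52% are kept with correlation 0, 64% with 0.5 and 70% with 0.7.

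**Step 5: sensitivity.** Fixing the number of words recalled and using other weights (8,000 draws per setting) gives this upward bias in mean ARC:

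| Weight | 5 words | 8 words | 12 words | 15 words |
|---|---|---|---|---|
| 1 (chance) | 0.57 | 0.26 | 0.21 | 0.14 |
| 2 (weak) | 0.38 | 0.13 | 0.09 | 0.04 |
| 4 (moderate) | 0.21 | 0.04 | 0.01 | 0.004 |
| 8 (strong) | 0.11 | 0.01 | 0.001 | 0.000 |

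If ARC were scored on joint recall of both lists (6 categories of 5), the bias is smaller. At chance the retained mean is 0.20 at 40% recall and 0.11 at 70%. At a true ARC near 0.35 the means of 0.38 and 0.33 become 0.43 and 0.34.

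**The case against.** The strongest reply is about size, not direction.

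- **The recall contrast is wide.** 40% versus 70% is 4.5 of 15 words. At 50% versus 70% the retained gap is about 0.09 at ARC 0.4 and 0.05 at ARC 0.6; at 70% versus 85% it is about 0.03 and 0.02.
- **Clustering may be strong.** Section 2.3.2 reports high rated familiarity and relevance (4.42 to 4.75 of 5), and each list has four learning cycles, so random recall order is not the obvious default. At a true ARC of about 0.75, only 4%, 2% and 0.4% of scores are negative at 40%, 50% and 70% recall, and at 70% the mean moves from 0.731 to 0.735.
- **Patient loss is doubly conditional.** It needs a complete-case ANOVA, which is not stated, and more than 15.9% negative scores per cell for a majority to go.
- **Shrinkage is not universal.** It holds at equal recall. If the better-clustered condition recalls fewer words, the gap can widen. If stimulation raises both recall and clustering, both distortions work against the study hypothesis.
- **Very short recalls can score below −1.** This is about 2% of scores at chance and 40% recall, with a minimum of −2.

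All of this stands as a limit on magnitude. None of it supports the rule. A single negative score may say little about one patient's strategy, but deleting only that tail still distorts the group mean. Joint scoring would soften the problem, but section 2.5 compares ARC between strategies, which calls for a score per list.

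**Conclusion.** The rule is wrong as written. The upward bias in mean ARC is certain whenever any score is negative, and at a given clustering strength it grows as fewer words are recalled. How far it alters the ARC comparisons cannot be known from the protocol. In the settings examined, the spurious gap caused by recall alone runs from about 0.02 (70% versus 85% recall, ARC 0.6) to 0.25 (40% versus 70%, chance), and a true difference of 0.22 at 50% recall falls to 0.14. These figures assume the standard ARC formula, per-list scoring and the stated recall and clustering levels. Loss of patients is a secondary risk that applies if clustering is weak and the ANOVA is complete-case. Because ARC is one of only two dependent variables and the exclusions are not counted, the ARC results cannot be relied on until they are re-run. The recall-rate analysis is untouched.

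**What to change.** Delete the exclusion from section 2.5 and state in its place:

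- All mathematically defined ARC scores are analysed, negative values included.
- Only undefined scores are missing, for example when every recalled word comes from one category or only one word per category is recalled.
- Numbers of negative and undefined scores are reported by arm, strategy and interval.
- The analysis without negative scores may be kept only as a labelled sensitivity analysis.

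Scores below −1 stay in. If a minimum recall count is wanted for stability, it should be set without regard to the sign of ARC and shown as a further sensitivity analysis. A linear mixed model, which keeps patients with an undefined cell, is optional.

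The study is completed, so the cost is a wording change, one re-run of the ARC analysis and a table of counts; no new data are needed. Reported ARC means will be lower. Undefined scores should be few: 5% at 40% recall, 1% at 50% and about none at 70%. They become common only with four or five words recalled and strong clustering (34% and 15% at weight 8 in step 5 of the working), which is a reason to report them.
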